8.8. Concomitant Medications

Concomitant medications will be coded to the Anatomical Therapeutic Classification using the WHO Drug Dictionary. The use of prior and concomitant medications taken during the study will be recorded on the CRFs. The use of concomitant medications during the study will be summarized by ATC1, ATC2 code and study group for the Safety population ([Table 12, Appendix A](#)) and a by-subject listing of prior and concomitant medication use will be prepared ([Listing 14, Appendix C](#)).

9. IMMUNOGENICITY

The analysis of immunogenicity will be performed on the Immunogenicity Population.

In general, descriptive statistics (mean and SD of \log_{10} titers, GMT and 95% CI, median, range) will be tabulated by treatment group and time-point. The two-sided 95% CI will be obtained using a *t*-distribution. Additionally, the geometric mean fold-rise from baseline (GMFR) will be computed (based on the difference in log titer of post-baseline measurement minus baseline) and summarized in the same manner. For GMTs and GMFRs, between-group comparisons will be examined with ANOVA. The normality of the log-transformed continuous outcomes will be assessed using goodness-of-fit tests based on the empirical distribution function and by inspection of the normal probability plot. If normality assumptions are not satisfied, then the Kruskal-Wallis test will be used.

The number and proportion of responders (subjects who seroconvert, i.e., ≥ 4 -fold increase in endpoint titer between baseline and post-vaccination samples), together with exact Clopper-Pearson 95% CIs will be tabulated by treatment group and time-point. If appropriate, between groups comparisons will be examined with Fisher's exact test unless assumptions are fulfilled for the χ^2 test.

In addition to the tables, reverse cumulative distribution (RCD) curves will be presented by parameter, visit and treatment group, for both GMTs and GMIs. For each parameter at each visit, the treatment groups will be presented by 4 RCD curves.

All statistical tests will be interpreted in a two-tailed fashion using $p < 0.05$ to represent statistical significance.

A listing of all immunogenicity results is provided in [Appendix C, Listing 6](#) through [Listing 12](#).

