11.9.4. Final Report

A final study report will be prepared in accordance with Guidance for Industry: Submission of Abbreviated Reports and Synopses in Support of Marketing Applications and ICH E3 Guideline

Structure and Content of Clinical Study Reports and provided to the sponsor for review and approval. The sponsor will use this report to prepare the submission to the FDA.

12. Statistics

Detailed statistical procedures, listings, table shells, and figures will be provided in a separate statistical analysis plan (SAP) written shortly after protocol approval but before any subject enrollment. The SAP will be finalized before study closeout and database lock. The following key statistical components will be considered, and a detailed description will be documented in the SAP:

- Primary and secondary endpoints and how they will be measured,
- Statistical methods and tests that will be used to analyze the endpoints,
- Strategy that will be used if the statistical test assumptions are not satisfied,
- Indication of whether the comparisons will be one-tailed or two-tailed (with justification of the choice) and the level of significance to be used,
- Identification of whether any adjustments to the significance level or the overall
- p value will be made to account for any planned or unplanned subgroup analyses or multiple testing,
- Specification of potential adjusted analyses and a statement of which covariates or factors will be included,
- Planned exploratory analyses and justification with their importance, and
- Any subgroup effects with biological justification and support from within and outside the study.

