12.1.2. Analysis Addressing the Secondary Study Objective

For immunology responses, both qualitative (responder rates) and quantitative (e.g., \log_{10} transformed values) results will be analyzed. Geometric mean titers will be calculated for serological responses along with their 95% confidence intervals (or standard deviation). If appropriate, between groups comparisons will be examined with nonparametric median tests (Kruskal-Wallis for continuous data and Fisher’s exact test for categorical data) unless assumptions are fulfilled for Student’s t or χ^2 .

Additional comparisons may be made using repeated measures analysis of variance with study group as the between subject factor and sample collection time-points as the repeated factor. Only subjects who receive at least 2 vaccine doses will be included in the immunology analysis. All statistical tests will be interpreted in a two-tailed fashion using an $\alpha=0.05$ to represent statistical significance.

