12.4. Procedures for Reporting Deviations from the Original Statistical Plan

Any deviation(s) from the original statistical plan as indicated in the protocol will be described in an amendment to the protocol and the SAP. Deviations from the SAP will be documented in accordance with NMRC SOPs.

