6. GENERAL STATISTICAL CONSIDERATIONS

6.1. General Principles

All analyses will be grouped by dose (2.5, 10, 25 µg, placebo). In general, all data will be listed, sorted by dose and subject, and when appropriate by visit number within subject. All summary tables will be structured with a column for each treatment group in order of increasing dose, with placebos pooled at the end, and will be annotated with the total population size relevant to that table, including any missing observations.

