6.4. Covariates and Subgroups

The protocol does not define any formal subgroup analyses, and the study is not adequately powered to perform subgroup analyses.

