	25 µg									
S. flexneri 2a Invaplex IgG										
	2.5 µg									
	10 µg									
	25 µg									
PBMCs for ALS										
S. flexneri 2a Invaplex IgA	2.5 µg									
	10 µg									
	25 µg									
S. flexneri 2a Invaplex IgG	2.5 µg									
	10 µg									
	25 µg									

¹ Analyzed by the lab and data available.

² Most recent observation prior to dose 1.

ALS: Antibody Lymphocyte Supematant; IgA: Immunoglobulin A; IgG: Immunoglobulin G.

A.2.1 Primary Immunology Outcomes

Table 14: Serologic IgA Responses to *S. flexneri* 2a Invaplex, Descriptive Statistics by Study Day and Treatment Group - Immunogenicity Population

Time Point	Statistic	InvaplexAR-DETOX Dose			Placebo (N=X)
		2.5 µg (N=X)	10 µg (N=X)	25 µg (N=X)	
Serum IgA					
Baseline	n	xx			
	Mean	xxx.x			
	Median	xxxx			
	SD	xxx.x			
	Range	xxxx, xxxx			
Day 22 Pre-Dose 2	n				
	Mean				
	Median				
	SD				
	Range				
	GMFR				
Repeat for	GMFR 95% CI				
	Day 43				
	Pre-Dose 3				
	Day 50				
	Post-Dose Day 7				
	Day 57				
	Post-Dose Day 14				
Day 71					
Post-Dose Day 28					

N = Number of subjects in the immunogenicity population. n = Number of subjects with data at the specified time point.

GMFR = Geometric Mean Fold-Rise from Baseline. SD = Standard Deviation. CI = Confidence Interval.

Table with similar in format to **Table 14**:

Table 15: Serologic IgG Responses to *S. flexneri* 2a Invaplex, Descriptive Statistics by Study Day and Treatment Group - Immunogenicity Population

Table 16: Antibody in Lymphocyte Supernatant (ALS) IgA Responses to *S. flexneri* 2a Invaplex, Descriptive Statistics by Study Day and Treatment Group - Immunogenicity Population

Time Point	Statistic	InvaplexAR-DETOX Dose			Placebo (N=X)
		2.5 µg (N=X)	10 µg (N=X)	25 µg (N=X)	
Serum IgA					
Baseline	n	xx			
	Mean	xxx.x			
	Median	xxxx			
	SD	xxx.x			
	Range	xxxx, xxxx			
Day 8 Post-Dose 1, Day 7	n				
	Mean				
	Median				
	SD				
	Range				
	GMFR				
	GMFR 95% CI				
Repeat for					
Day 29 Post-Dose 2, Day 7					
Day 50 Post-Dose 3, Day 7					
Day 71 Post-Dose 3 Day 28					

N = Number of subjects in the immunogenicity population. n = Number of subjects with data at the specified time point.

GMFR = Geometric Mean Fold-Rise from Baseline. SD = Standard Deviation. CI = Confidence Interval.

Table with similar in format to **Table 16**:

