Table 17: Antibody in Lymphocyte Supernatant (ALS) IgG Responses to *S. flexneri* 2a Invaplex, Descriptive Statistics by Study Day and Treatment Group - Immunogenicity Population

Table A1: Serologic Responses to *S. flexneri* 2a Invaplex, Geometric Mean Titer by Study Day and Treatment Group - Immunogenicity Population [In-text]

Note: Tables A1–A4 are in-text. Table numbers will be adjusted when compiling the CSR.

Time Point	Statistic	InvaplexAR-DETOX Dose			Placebo (N=X)	P-Value
		2.5 µg (N=X)	10 µg (N=X)	25 µg (N=X)		
Serum IgA						
Baseline	n	XX				X.XXXX
	GMT	XXXX				
	95% CI	XXXX - XXXX				
Day 22 Pre-Dose 2						X.XXXX
Day 43 Pre-Dose 3						X.XXXX
Day 50 Post-Dose Day 7						X.XXXX
Day 57 Post-Dose Day 14						X.XXXX
Day 71 Post-Dose Day 28						X.XXXX
Serum IgG						
Baseline	n	XX				X.XXXX
	GMT	XXXX				
	95% CI	XXXX - XXXX				
Day 22 Pre-Dose 2						X.XXXX
Day 43 Pre-Dose 3						X.XXXX
Day 50 Post-Dose Day 7						X.XXXX
Day 57 Post-Dose Day 14						X.XXXX
Day 71 Post-Dose Day 28						X.XXXX

GMT = Geometric Mean Titer. CI = Confidence Interval. P-values are from ANOVA tests of differences between groups in mean log titers.

Table A2: Serologic Responses to *S. flexneri* 2a Invaplex, Seroconversion Rates by Study Day and Treatment Group - Immunogenicity Population [In-text]

Time Point	Statistic	InvaplexAR-DETOX Dose			Placebo (N=X)	P-Value
		2.5 µg (N=X)	10 µg (N=X)	25 µg (N=X)		
Serum IgA						
Day 22 Pre-Dose 2	n	xx				x.XXXX
	Seroconversion %	xx.x				
	95% CI	xx.x, xx.x				
Day 43 Pre-Dose 3						x.XXXX
Day 50 Post-Dose Day 7						x.XXXX
Day 57 Post-Dose Day 14						x.XXXX
Day 71 Post-Dose Day 28						x.XXXX
Serum IgG						
Day 22 Pre-Dose 2						x.XXXX
Day 43 Pre-Dose 3						x.XXXX
Day 50 Post-Dose Day 7						x.XXXX
Day 57 Post-Dose Day 14						x.XXXX
Day 71 Post-Dose Day 28						x.XXXX

Seroconversion defined as ≥ 4 -fold increase in titer from baseline. CI = Exact Clopper Pearson Confidence Interval. P-values are from Fisher's exact 2-tail tests of differences between groups in seroconversion rates.

Table A3: Antibody in Lymphocyte Supernatant (ALS) Responses to *S. flexneri* 2a Invaplex, Geometric Mean Titer by Study Day and Treatment Group - Immunogenicity Population [In-text]

Time Point	Statistic	Invaplex _{AR} -DETOX Dose			Placebo (N=X)	P-Value
		2.5 µg (N=X)	10 µg (N=X)	25 µg (N=X)		
ALS IgA						
Baseline	n	xx				x.XXXX
	GMT	xxxx				
	95% CI	xxxx - xxxx				
Day 8 Post-Dose 1, Day 7						x.XXXX

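### The SAP plans no baseline-adjusted titer comparison, its shells print no p-value for the planned fold-rise test, and SAP 6.4 names no covariate: a cheap precision gain on secondary comparisons

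*SAP*

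**What the plan says.** SAP section 9 plans two continuous between-group comparisons at each time point: "For GMTs and GMFRs, between-group comparisons will be examined with ANOVA". The Kruskal-Wallis test is the fallback if normality fails. The fold-rise (GMFR) is the post-baseline log titer minus the baseline log titer.

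The Appendix A shells carry only part of this. Tables A1 (serum) and A3 (ALS) have a p-value column with the footnote "P-values are from ANOVA tests of differences between groups in mean log titers". Tables 14 to 17 show the fold-rise ("GMFR = Geometric Mean Fold-Rise from Baseline") with a 95% CI but no p-value. Tables A2 and A4 give Fisher p-values for the proportion with at least a 4-fold rise.

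On covariates, protocol section 12 lists as SAP content: "Specification of potential adjusted analyses and a statement of which covariates or factors will be included". The whole of SAP 6.4, headed Covariates and Subgroups, reads: "The protocol does not define any formal subgroup analyses, and the study is not adequately powered to perform subgroup analyses". Protocol 12.1.2 adds an optional analysis, "Additional comparisons may be made using repeated measures analysis of variance", which SAP 9 does not take up.

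Under SAP 6.3.2, subjects without a baseline value are excluded from the immunogenicity population. Cohorts are enrolled in sequence (SAP 4.4.5). Tables run "in order of increasing dose, with placebos pooled at the end" (SAP 6.1).

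**The concern.** A raw log-titer comparison leaves each subject's starting level in the error term, and any baseline difference between groups in the estimate. A fold-rise comparison removes the starting level but adds noise when baseline and post-vaccination titers are weakly related. Regressing the post-vaccination titer on group and baseline (ANCOVA) uses baseline only as far as it is informative. The data are already collected, but no such model is planned. The one planned continuous test that does use baseline has no place for its p-value in the shells.

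At stake are the precision of the secondary immunogenicity comparisons and how they read if groups start at different levels by chance. Dose escalation rests on safety alone, and the two hypotheses of at least 50% responders are judged on responder proportions, so neither is affected.

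**Working it through.** **Plan's own figure.** The only sample-size figure is the 95% CI of 0-21% for 0 events in 16. It reproduces: 1 − 0.025^(1/16) = 20.6%. It bears on this point only by fixing 16 per dose group.

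**Inputs from the documents.** Groups of 16/16/16 plus 12 pooled placebo (SAP 4.4.3, 6.1); two-sided 0.05 (SAP 9).

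**Assumed inputs.** The documents give no titer SD, effect size, baseline-to-post correlation (ρ) or share of baselines below the starting dilution. I use unit SD, true shifts over placebo of 0.4/0.7/1.0 SD, and ρ of 0.3/0.5/0.7.

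**Residual variance**, relative to the raw-titer test: raw titer 1; fold-rise 2(1 − ρ); ANCOVA 1 − ρ².

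**Noncentrality.** The weighted mean shift is 16 × (0.4 + 0.7 + 1.0)/60 = 0.56. For the raw titer, λ = 16 × (0.16² + 0.14² + 0.44²) + 12 × 0.56² = 3.82 + 3.76 = 7.58. The other tests divide this by their variance.

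| ρ | Raw titer: λ, power | Fold-rise: λ, power | ANCOVA: λ, power |
|---|---|---|---|
| 0.3 | 7.58, 59.5% | 5.42, 44.5% | 8.33, 63.9% |
| 0.5 | 7.58, 59.5% | 7.58, 59.5% | 10.11, 73.3% |
| 0.7 | 7.58, 59.5% | 12.64, 83.3% | 14.87, 89.2% |

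Simulation (20,000 trials per setting) gives about 60/59/60%, 45/59/84% and 63/72/89%. The closed form slightly flatters ANCOVA because it ignores the cost of chance baseline differences. At ρ = 0, ANCOVA has 58% and the raw titer 59%.

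**Baselines below the starting dilution**, set to half of it as SAP 3.3.6 requires (SD 0.5 log10 assumed). Power at ρ 0.3/0.5/0.7:

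| Share below | Raw titer | Fold-rise | ANCOVA |
|---|---|---|---|
| 50% | 55/55/54% | 43/56/76% | 57/65/79% |
| 80% | 41/41/41% | 35/42/56% | 42/46/55% |
| 90% | 29/29/29% | 26/31/38% | 29/31/36% |

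**No true difference.** All three tests reject about 5% of the time overall. Among the fifth of simulated trials with the largest chance baseline imbalance, at ρ 0.5/0.7/0.9 the raw-titer test rejects 10/16/23%, the fold-rise test 11/9/6% and ANCOVA about 5%.

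**Systematic difference.** One dose group starts 0.5 SD higher and the vaccine has no effect. Rejection at ρ 0.3/0.5/0.7:

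| Post-vaccination shift | Raw titer | Fold-rise | ANCOVA |
|---|---|---|---|
| ρ × 0.5 SD | 7/10/14% | 11/10/7% | 5/5/5% |
| 0.5 SD, persists in full | 26/25/26% | 5/5/5% | 14/11/8% |
| none, disappears fully | 5/5/5% | 19/26/41% | 7/11/22% |

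Each test holds 5% in one row only.

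**The case against.** The case against is substantial.

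- **Baseline is already used.** The fold-rise ANOVA is in the SAP text, and the 4-fold responder tests have p-value columns. Tables A1 and A3 print baseline GMTs directly above the later rows. SAP section 1 presents the shells as samples, so a missing column does not cancel a planned test. This stands: for the fold-rise the defect is a mismatch between text and shell, and only the covariate-adjusted model is absent from the plan.
- **The study is descriptive.** SAP 4.2 says placebo serves mainly for blinding rather than as an immunogenicity comparator, and that the study was not designed to show group differences. This stands and limits the weight of the point. It argues against making dose-to-placebo ratios a headline result.
- **More tests bring more ambiguity.** With three tests per isotype and day, at least one rejects in about 10% of null trials. The two planned tests alone give about 9%. SAP 6.7 applies no multiplicity adjustment. The answer is to name the main comparison.
- **The protocol wording is permissive.** It speaks of potential adjusted analyses, and the repeated-measures analysis is optional. That is fair, but a sentence saying whether any covariate is used is still missing.

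A reader might go further and infer that sequential enrolment makes the raw-titer test misleading whatever happens to a baseline difference, and that ANCOVA cures this. Neither follows. Between-dose contrasts are not randomised, and 12 − 4 = 8 of the 12 planned placebo subjects in each dose-to-placebo contrast come from other cohorts. But when a baseline shift disappears fully, the raw-titer test is the only one that holds 5%. The documents report no baseline difference, and all cohorts share one site and one anti-LPS ceiling.

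**Conclusion.** The point holds as a precision and chance-imbalance improvement on secondary, unpowered comparisons. The planned tests are not invalid, and nothing in the documents shows their error rate to be inflated. Against the better of the two planned tests, ANCOVA adds about 3, 13 and 5 percentage points of power at ρ 0.3/0.5/0.7. With 80% of baselines below the starting dilution, the difference is about +1, +4 and −1. These figures rest on assumed SD, effect, correlation and floor; the text-to-shell gap and the silence on covariates do not. Adjustment is no remedy for confounding between sequential cohorts, because which test is protected depends on how a baseline difference carries forward.

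**What to change.** Settle these before the Day 71 group-level unblinding (SAP 6.2):

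1. **SAP 6.4.** Name baseline log10 titer of the same assay and isotype as the only covariate.
2. **SAP 9.** Add an ANCOVA of post-baseline log10 titer on treatment group and baseline log10 titer. State that it is the main continuous between-group comparison, with the planned raw-titer and fold-rise ANOVAs and the Kruskal-Wallis fallback as supportive. Decide once per assay and isotype, from the baseline data, whether the covariate is dropped because nearly all baselines are below the starting dilution. Write the threshold down; fewer than 10% measurable (6 of 60) is one possibility. A decision per time point would let the model change from visit to visit.
3. **Shells.** Add the ANCOVA p-value to Tables A1 and A3, and print the already planned fold-rise p-value in Tables 14 to 17.
4. **Interpretation.** State that between-dose contrasts compare sequential cohorts and are not randomised. Treat any adjusted dose-to-placebo ratios as optional and descriptive.

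**Cost.** One degree of freedom and the assumptions of linearity and a common slope. There are 2 × 5 serum and 2 × 4 ALS isotype-by-day combinations, so 18 ANCOVA and 18 fold-rise p-values are added, without multiplicity adjustment. No new data are needed and no subject is lost. Protocol 12.1.2 does not mention ANCOVA, and protocol 12.4 says: "Any deviation(s) from the original statistical plan as indicated in the protocol will be described in an amendment to the protocol and the SAP". If the addition counts as such a deviation, it should be recorded that way.

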9.1. Primary Immunogenicity Analysis

The immunogenicity endpoints listed in Section 3.2.2 will be summarized as above in [Table 14](#) through [Table 17](#), and in [Figure 2](#) through [Figure 9](#) to meet the secondary objective of assessing IgG and IgA serologic and ALS responses to *S. flexneri* 2a Invaplex. Complete listings will be presented in [Listing 6](#) (serum IgA), [Listing 7](#) (serum IgG), [Listing 8](#) (ALS IgA) and [Listing 9](#) (ALS IgG) in [Appendix C](#).

9.2. Exploratory Immunogenicity Analyses

Analysis of exploratory endpoints is beyond the scope of this SAP.

10. REPORTING CONVENTIONS

P-values will be reported to 3 decimal places; p-values less than 0.001 will be reported as “<0.001” and p-values greater than 0.999 will be reported as “>0.999”. The median (except for ties), minimum and maximum will be reported on the same scale as the original data. The mean, standard deviation and CIs will be reported to one additional decimal place. Percentages will be reported to one decimal and corresponding 95% CIs will be to two decimals.

11. TECHNICAL DETAILS

SAS version 9.3 or above will be used to generate all tables, figures and listings.

12. SUMMARY OF CHANGES IN THE CONDUCT OF THE STUDY OR PLANNED ANALYSES

No changes have been made at this time.

Table 22: Subjects Experiencing AEs Related to Study Product Up to and Including Visit 11 (Day 28 Post-Dose 3), by MedDRA® Preferred Term (PT), Severity and Treatment Group - Safety Population [In-Text, by PT only].....	47
Table 23: Subjects Experiencing AEs Post-Dose 1 and Prior to Dose 2, by MedDRA® System Organ Class (SOC), Preferred Term (PT), Severity and Treatment Group - Safety Population	47
Table 24: Subjects Experiencing AEs Related to Study Product, Post-Dose 1 and Prior to Dose 2, by MedDRA® System Organ Class (SOC), Preferred Term (PT), Severity and Treatment Group - Safety Population.....	47
Table 25: Subjects Experiencing AEs Post-Dose 2 and Prior to Dose 3, by MedDRA® System Organ Class (SOC), Preferred Term (PT), Severity and Treatment Group - Safety Population	47
Table 26: Subjects Experiencing AEs Related to Study Product, Post-Dose 2 and Prior to Dose 3, by MedDRA® System Organ Class (SOC), Preferred Term (PT), Severity and Treatment Group - Safety Population.....	47
Table 27: Subjects Experiencing AEs Up to 28 Days Post-Dose 3, by MedDRA® System Organ Class (SOC), Preferred Term (PT), Severity and Treatment Group - Safety Population	47
Table 28: Subjects Experiencing AEs Related to Study Product, Up to 28 Days Post-Dose 3, by MedDRA® System Organ Class (SOC), Preferred Term (PT), Severity and Treatment Group - Safety Population.....	47
Table 29: Grade 2 or Greater Non-Serious Adverse Events [In-Text]	48
Table 30: Deaths, Serious Adverse Events and Other Significant AEs [In-Text]	48
Table 31: Hematology and Serum Chemistry Test Results, Descriptive Statistics by Treatment Group - Safety Population	49
Table 32: Final On Therapy Hematology and Serum Chemistry Severity Grading, by Treatment Group and Relationship ¹ to IP - Safety Population.....	50
Table 33: Vital Signs: Descriptive Statistics by Visit and Treatment Group - Safety Population	51
Table 34: Summary of Abnormal Physical Exam Findings Prior to Dose 1 – Safety Population	52

A.1 Demographics Tables**9.1 Overall Study Design and Plan Description****Table 1: Study Design [In-Text]**

Cohort	Group	N	Route	Study Dose	Timing of Injections
A	A-1	16	IM	InvaplexAR-DETOX 2.5 µg	Day 1, 22, 43
	A-2	4	IM	Placebo	Day 1, 22, 43
B	B-1	16	IM	InvaplexAR-DETOX 10 µg	Day 1, 22, 43
	B-2	4	IM	Placebo	Day 1, 22, 43
C	C-1	16	IM	InvaplexAR-DETOX 25 µg	Day 1, 22, 43
	C-2	4	IM	Placebo	Day 1, 22, 43

IM = intramuscular.

Immunogenicity and Safety Measurements Assessed

Table 2: Clinical Protocol Time and Events Schedule [In-Text]

Visit Number	00A	00B	01	02	03	04	05	06	07	08	09	10	11	12
Study Event	Screening	-7 ¹	1	2	8	22	23	29	43	44	50	57	71 ²	223
Post-Dose Day			0	1	7	21/0	1	7	21/0	1	7	14	28	180
Compliance Ranges (days)	-60 to -9	-14 to -2	N/A	N/A	±1	±2	N/A	±2	±2	N/A	±3	±3	±4	±28
Study Briefing	X	X												
Comprehension Assessment	X													
Informed Consent (Study Participation)	X													
Informed Consent (HIV Testing)	X													
Screening Medical History/ Physical Exam	X													
CBC and Serum Chemistry ³	X	X												
C-Reactive Protein			X	X										
Anti-HIV-1/2			X											
HLA-B27	X													
HBs Ag		X												
Anti-HCV		X												
Serum IgA	X													
Anti LPS Antibody Screening	X													
Vital signs (BP, HR, T)	X	X	X	X	X	X	X	X	X	X	X	X	X	X
Urine pregnancy test	X		X											
Dose		X												
Clinical Check ⁴	X	X	X	X	X	X	X	X	X	X	X	X	X	X
Symptom Diary ⁵		X	X	X	X	X	X	X	X	X	X	X	X	X
Serology ⁶		X												
Peripheral Blood Mononuclear Cells (PBMCs) ⁷	X	X	X	X	X	X	X	X	X	X	X	X	X	X
Fecal IgA		X	X	X	X	X	X	X	X	X	X	X	X	X
Additional Sample Collections ⁸		X	X	X	X	X	X	X	X	X	X	X	X	X
Study Completion														
Post-Study Safety Assessment ⁹														
Blood Volume (mL) by Study Day	25	82	74	4	70	10	0	67	10	0	77	10	70	0

¹ Day -7 stool range is -14 to -2.

² The data will be locked following entry of the Day 71 data

³ Chemistry includes serum electrolytes, glucose, BUN, creatinine, AST, ALT, CBC and chemistry will not be repeated if the screening visit occurs during the Day -14 to -9 window.

⁴ Clinical checks on dose days include pre- and post-dose complete assessments including targeted physical exams (volunteers will be observed for 30 minutes post-dose), baseline exam, and physical assessment.

⁵ Volunteer diaries post-dose will begin day of dose through the 7-day post-dose follow-up for each dose.

⁶ Samples taken from blood draw for that day, serum samples will be assayed for antibody (IgG and IgA) titers against *S. flexneri* 2a LPS, IgA, IgC, and *S. flexneri* 2a Invaplex by previously established methods.

⁷ PBMCs include collection for Antibody Secreting Cells (ASC), Antibody Lymphocyte Supematant (ALS), memory B and T cells and α 4 β 7+ B cells. A missed PBMC collection on Day -7 will not be considered a protocol deviation.

⁸ Additional sample collections may include saliva.

⁹ Day 223 assessments will be performed via telephone.

